### **Origin of the data**

The source document for this study will be the patient's medical records documented in his/her medical chart, including his/her surgical records, which will be kept at the study site. For special issues and/or queries or government inspection requirements, it will also be necessary to access the complete study file, if the patients' right to anonymity is protected.

The information collected in CRFs must match the data from the Medical charts.

**Cohort treatment/labelling**

For the study, “long-term responders to axitinib” have been defined as patients with a PFS for at least 9 months with the drug, and “refractory patients to axitinib” have been defined as patients with disease progression in the first assessment since the initiation of treatment (estimated PFS  $\leq 3$  months).

See point 5.2. *subgroups*, and in group 7 *Definition of variables and objectives*, how these groups are defined in terms of CRFs variables and algorithmic conditions of computer programming for the patient’s classification.

## 2.2 STUDY OBJECTIVES

The primary objective of the study is:

- To describe the baseline clinical characteristics of the long-term responders to axitinib and to identify clinical factors associated with a long-term response to axitinib (defined as progression-free survival of at least 9 months since the drug initiation), by comparing two groups of patients with an extreme response to the drug: one group of patients who are progression-free for at least 9 months versus a group of patients with disease progression before the first response assessment.
- To analyse the association of some clinical factors with greater benefit with the drug.

The secondary objectives of the study are:

- To describe the response to treatment with axitinib in the long-term responder's group.
- To describe the efficacy for each treatment line (second line treatment and further lines).
  - Best treatment response (Complete response [CR], Partial response [PR], Stable disease [SD]).
  - Progression-free Survival.
  - Objective Response Rate (ORR) and Clinical Benefit (sum of CR, PR and SD).
  - Time to progression.
  - Overall Survival.
- To describe the duration of treatment with axitinib.
- To describe the percentage of patients who increased axitinib doses to more than 5 mg twice daily.
- To describe the percentage of patients who reduced axitinib doses to less than 5 mg twice daily.
- To describe the axitinib tolerability.
- To describe the treatments received at progression.
- To describe the response to the treatments received at progression.

### **3 INTERIM ANALYSES**

No interim analyses are planned.

### **4 HYPOTHESIS AND DECISION RULES**

The level of significance will be  $\alpha=0.05$  two-tailed in all the statistical inference tests. Adjustment by multiple comparisons is not planned.

### **5 ANALYSIS GROUPS/POPULATIONS**

#### **5.1 FULL ANALYSIS SET**

The full analysis set [FAS] includes all evaluable patients, i.e. all patients who meet all the inclusion criteria and none of the exclusion criteria and have received at least one dose of axitinib prior to inclusion in the study.

#### **5.2 SUBGROUPS**

For some of the study objectives, the following two groups of patients with extreme responses to the drug are defined (see definition in point 7. Definition of variables):

- “Long-term responders to axitinib”: Patients who have a PFS of at least 9 months with the drug.
- “Patients primary refractory to axitinib”: Patients with disease progression at the first assessment after the initiation of treatment (estimated PFS  $\leq 3$  months). It means, patients with best response to axitinib=PD.

## 6 VARIABLES IN THE CRF

The following groups of variables will be recorded for this observational study: Demographic data, medical history, first-line treatments, other treatments prior to axitinib, treatment with axitinib, subsequent treatments and the patient's vital status. Details of all the variables recorded in the CRF are given below:

- Demographic data:
  - Date of birth
  - Gender
- Clinical history of renal cell carcinoma
  - Date of first diagnosis
  - Tumour stage at disease diagnosis (I/II/III/IV)
  - Non-systemic treatment
    - Nephrectomy (Yes/No/Unknown).
      - If yes, specify:
        - Date (Date/Unknown)
        - Type (Total/Partial/Unknown)
        - Kidney (Right/Left/Unknown)
      - Radiotherapy (Yes/No/Unknown).
        - If yes, specify:
          - Date (Date/Unknown)
      - Histological type (100% Clear cells/ Primarily clear cells/ Primarily non-clear cells/ 100% Non-clear cells)
        - If 100% Clear cells have not been marked, specify (Sarcomatoid/Chromophobe/ type 1 Papillary/ type 2 Papillary/ Other, specify/Not performed)
    - Diagnosis of advanced disease
      - Date
      - Stage (III/IV)
      - Metastasis site (multi-response question):
        - Lymph nodes
        - CNS
        - Liver
        - Lungs
        - Bone
        - Other, specify
      - Risk criteria before the initiation of the first line
        - Time from initial diagnosis to systemic treatment less than 1 year (Yes/No/Unknown)
        - ECOG/PS (Yes/No/Unknown)
        - LDH >1.5 x ULN (Yes/No/Unknown)
        - Haemoglobin < LLN (Yes/No/Unknown)
        - Corrected calcium >10 mg/dl (Yes/No/Unknown)
        - Presence of 2 or more metastatic sites (Yes/No/Unknown)

- 
- Platelets > ULN (Yes/No/Unknown)
  - Neutrophils > ULN (Yes/No/Unknown)- (current value)
  - Lymphocytes (Yes/No/Unknown)- (value)
  - Smoking habits (Smoker/Non-smoker/Former smoker)
  - First-line treatment
    - Drug
    - Starting dose
    - Duration of treatment
      - Start date
      - End date
      - Reason for treatment withdrawal (DP/Toxicity/Other, specify)
      - Has there been disease progression? (No/Yes, specify date)
      - Best treatment response (CR, PR, SD, DP/Not evaluable).
        - Date of the best response obtained
  - Other treatments prior to axitinib
    - Has the patient received other treatments prior to axitinib? (Yes/No/Unknown)
      - If yes, specify:
        - 2nd-line treatment
          - Drug
          - Starting dose
          - Reason for starting this treatment (DP in the 1st line treatment/Toxicity in the 1st line treatment/Other, specify)
          - Start date
          - End date
          - Reason for treatment withdrawal (DP/Toxicity/Other, specify)
          - Has there been disease progression? (No/Yes, specify date)
          - Best treatment response (CR, PR, SD, DP/Not evaluable).
            - Date of the best response obtained
        - 3rd-line treatment
          - Drug
          - Starting dose
          - Reason for starting this treatment (DP in the 2nd line treatment/Toxicity in the 2nd line treatment/Other, specify)
          - Start date
          - End date
          - Reason for treatment withdrawal (DP/Toxicity/Other, specify)
          - Has there been disease progression? (No/Yes, specify date)

- 
- Best treatment response (CR, PR, SD, DP/Not evaluable).
    - Date of the best response obtained
  - Treatment with axitinib
    - Treatment line in which it was received.
    - Reason for starting treatment with axitinib (DP in previous treatment line/Toxicity in previous treatment line/Other, specify).
    - Risk criteria at the initiation of treatment with axitinib
      - Time from first diagnosis to systemic treatment less than 1 year (Yes/No/Unknown)
      - ECOG/PS (current status) (Yes/No/Unknown)
      - LDH >1.5 x ULN (Yes/No/Unknown)
      - Haemoglobin < LLN (Yes/No/Unknown)
      - Corrected calcium >10 mg/dl (Yes/No/Unknown)
      - Presence of 2 or more metastatic sites (Yes/No/Unknown)
      - Platelets > ULN (Yes/No/Unknown)
      - Neutrophils > ULN (Yes/No/Unknown) (value)
      - Lymphocytes (Yes/No/Unknown) (value)
      - Smoking habits (Smoker/Non-smoker/Former smoker)
    - Presence of comorbidities
      - Kidney failure (Yes/No)
        - If yes, specify, Creatinine Clearance (Mild, 60-89 ml/min/ Moderate, 30-59 ml/min/ Severe, 15-29 ml/min/ End Stage, <15 ml/min/ Dialysis)
      - Liver failure (Yes/No)
        - If yes, specify, Child Pugh (A/B/C)
      - Cardiovascular (Yes/No)
        - If yes, specify (multi-response question)
          - Decreased LVEF, specify %
          - Heart failure
          - Previous arrhythmia
          - Previous ischaemia
          - Controlled HTN, specify number of antihypertensive agents
          - Other, specify
      - Respiratory disease (Yes/No), specify
      - Other comorbidity (Yes/No), specify
    - Start date of treatment with axitinib
    - Has treatment with axitinib been discontinued? (Yes/No)
      - If yes, specify:
        - End-of-treatment date
        - Reason for suspension of treatment (DP/Toxicity/Other, specify)
    - Risk criteria at discontinuation of treatment with axitinib

- 
- Time from first diagnosis to systemic treatment less than 1 year (Yes/No/Unknown)
    - ECOG/PS (current status) (Yes/No/Unknown)
    - LDH >1.5 x ULN (Yes/No/Unknown)
    - Haemoglobin < LLN (Yes/No/Unknown)
    - Corrected calcium >10 mg/dl (Yes/No/Unknown)
    - Presence of 2 or more metastatic sites (Yes/No/Unknown)
    - Platelets > ULN (Yes/No/Unknown)
    - Neutrophils > ULN (Yes/No/Unknown) (value)
  - Has there been disease progression? (No/Yes, specify date)
  - Best treatment response (CR, PR, SD, DP/Not evaluable).
    - Date of the best response obtained
  - Starting dose (5 mg/12 h; 2 mg/12 h; 3 mg/12 h; 7 mg/12 h; 10 mg/12 h)
  - Has the dose been modified? (Yes/No)
    - If yes, specify:
      - Increased/Reduced
      - Dose modification date
      - Reason for dose modification
      - New dose (5 mg/12 h; 2 mg/12 h; 3 mg/12 h; 7 mg/12 h; 10 mg/12 h; other, specify mg/h)
  - Adverse events
    - Adverse events (Anaemia; Asthenia; Fatigue; Diarrhoea; Dysphonia; Elevated ALT/GPT; Elevated AST/GOT; Elevated Bilirubin; Elevated Creatinine; Elevated Haemoglobin; Elevated Lipase; Hypercalcaemia; Hypertension; Hypocalcaemia; Hypophosphatemia; Hypothyroidism; Lymphopenia; Mucositis; Nausea; Neutropenia; Proteinuria; Rash; Hand-foot syndrome; Thrombocytopenia; Vomiting, Other, specify).
    - Worst grade according to CTCAE
    - Cycle in which the worst grade occurred
    - Related to treatment (Yes/No)
    - Serious AE? (Yes/No), if yes, specify
      - Reason (Results in death/ Is life threatening/ Leads to hospitalisation or prolongation of hospitalisation/ Causes persistent or significant disability or incapacity/ Causes a congenital anomaly or birth defect/ Is medically significant).
  - Subsequent treatments
    - Has the patient received any subsequent treatment? (Yes/No)
      - If yes, specify
        - Drug received
        - Starting dose
        - Treatment line
        - Start date

- End date
- Ongoing
- Best response attained (CR, PR, SD, DP/Not evaluable)
- Reason for discontinuation (DP/Toxicity/Other, specify)
- Vital status
  - Date of last follow-up
  - Status (Alive/Death)
    - If Death, specify
      - Date of death
      - Cause of death (DP, Other, specify)

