## 5. MILESTONES

In order to obtain enough information to perform a proper analysis of the data, the proposed work plan is as follows:

Once the study is approved by the competent authorities and the contracts have been signed at each site, each study site will be opened and the investigator may start recording the requested data in the electronic case report form.

Before including the patient in the study, the investigator should review and verify the inclusion/exclusion criteria.

The observation period—given that it is an observational, retrospective study—will always be prior to the inclusion of the patient in the study, with this starting at the time of diagnosis of the study condition (renal cell carcinoma) and ending at the time of inclusion in the study, or the death of the patient if this occurs first.

[figure not shown]
The person appointed by the sponsor to monitor the study may request a face-to-face or remote visit from the site for the review of the data reported in the eCRF at any time after the first patient is included.

The site undertakes to fill in the data in the CRFs, and to resolve any discrepancies that may arise in them, on a regular basis and without interfering with the study’s planned schedule.

The study sponsor will regularly inform the investigators involved in the study on its status by sending electronic monitoring reports.

The administrative procedures for the study with the central IEC and the AEMPS are expected to start in September/October 2017, so the following schedule is being considered:

Milestone	Expected date
Date of approval from the central IEC	7 NOVEMBER 2017
Start of data collection Date of opening of the first site and start of study recruitment	15 MARCH 2018
End of recruitment period Expected date of study recruitment closure	30 SEPTEMBER 2018
End of data collection	30 DECEMBER 2018

Expected date of closing of study data collection	
Final results report Expected date for the final results of the study	31 MARCH 2019

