## 7 DEFINITION OF VARIABLES AND OBJECTIVES

In addition, the following variables will be calculated from the CRF data:

NOTE: In patients with dates after the date of the IC visit / signature, the date of the IC visit / signature has been considered as the date of the last check. Due to the retrospective nature of the study, no data can be collected after the patient was included in the IC study / signature.

- Age (years) of patient at time of visit= (Visit date – Date of birth) / 365.25
- Age (years) at first diagnosis= (Date of first diagnosis – Date of birth) / 365.25
- Age (years) at the initiation of axitinib= (start date of axitinib – Date of birth) / 365.25
- Number of metastatic locations = sum (Lymph nodes, CNS, Hepatic, Pulmonary, Bone, Other).
- • Neutrophil / lymphocyte ratio. It will be categorized as follows:  $\leq 3$ ,  $> 3$ . "Before the beginning of the first line" and "At the beginning of treatment with axitinib" will be analyzed. This ratio is not calculated on axitinib suspension because there is no current lymphocyte value data in that part of the CRF.
- Time (months) between first diagnosis and nephrectomy = (Date of nephrectomy – Date of first diagnosis) / 30.4375. A list with the information (site, patient, date of first diagnosis, date of nephrectomy and the calculated time) in cases in which the time is negative (with date of nephrectomy before or equal to date of first diagnosis) will be displayed, and these cases will not be included in the descriptive analysis
- Time (months) between first diagnosis and radiotherapy = (Date of radiotherapy – Date of first diagnosis) / 30.4375. A list with the information (site, patient, date of first diagnosis, date of radiotherapy and the calculated time) in cases in which the time is negative (with date of radiotherapy before or equal to date of first diagnosis) will be displayed, and these cases will not be included in the descriptive analysis.
- Time (months) between first diagnosis and 1st-line treatment = (Date of the initiation of 1st-line treatment – Date of first diagnosis) / 30.4375. A list with the information (site, patient, date of first diagnosis, date of 1st-line treatment and the calculated time) in cases in which the time is negative (with date of 1st-line treatment before or equal to date of first diagnosis) will be displayed, and these cases will not be included in the descriptive analysis

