## 7.1 PRIMARY OBJECTIVE

In order to meet the study's primary objective, the baseline clinical characteristics of two patient groups with extreme response to the drug will be compared: A group of patients with long-term responses to the drug (long-term responders to axitinib) versus a group of patients with disease progression at the first assessment after the initiation of treatment (group of patients refractory to axitinib).

The classification (in long-term responders or refractory patients) will be based on PFS (in months), as indicated in section 5.2.

It will be shown the following descriptive tables:

- “Long responder” patient (Yes, No). “Long responding patient” is defined if he / she has an PFS  $\geq 9$  months (during axitinib treatment). The 95% CI will be displayed.
- PFS in long responding patients. Only the descriptive analysis of the time in months and the CI for the average, will be shown.
- “Refractory” patient (Yes, No). "Refractory patient" is defined if there is a better response to treatment = PE (to axitinib treatment). 95% CI will be shown.
- PFS in refractory patients. Only the descriptive analysis of the time in months and the CI for the average will be shown.
- Patient group (Long respondent, refractory). It is defined in section 5.2. IC95% will be displayed

At the same time, In addition to comparisons of baseline clinical characteristics between the groups (long-term responders, refractory patients), an association analysis of the following factors with the study groups will be performed:

- Age with respect to first visit ( $\leq 65$  years and  $> 65$  years).
- Age with respect to first diagnosis ( $\leq 65$  years and  $> 65$  years).
- Age with respect to start of axitinib ( $\leq 65$  years and  $> 65$  years).
- Baseline ECOG/PS and at the initiation of first line treatment (0, 1 and  $\geq 2$ ).
- Baseline ECOG/PS and at the initiation axitinib treatment (0, 1 and  $\geq 2$ ).
- Baseline ECOG/PS and at the end of axitinib treatment (0, 1 and  $\geq 2$ ).
- Number of previous treatment lines
- Number of previous treatment lines (1, 2 and  $\geq 3$ )
- Previous nephrectomy (yes and no)
- MSKCC (or IMDC) risk group in all moments in which it is analysed during the study (favourable, intermediate and poor)

- Histology (100% clear cells, primarily clear cells, primarily non-clear cells, 100% non-clear cells)
- Duration of first-line treatment

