## 9.2 STATISTICAL ANALYSES

### Primary objective

A descriptive analysis will be performed of the baseline clinical characteristics (clinical history of renal cell carcinoma, first-line treatment, other treatments prior to axitinib) of the population of patients who are long-term responders with axitinib, in those patients refractories to treatment, and overall.

The baseline clinical characteristics will be statistically compared according to membership to each one of the two extreme treatment response groups.

Efficacy variables will be analyzed and compared between groups of long responders and refractory patients: PFS, time to progression, overall survival, overall survival from the beginning of the 1st line. These analyzes will be added in the statistical report in the sections in which these same analyzes are shown for the total N of patients.

In addition, the association of clinical factors of interest with the benefit of treatment will be analysed by logistic regression (see point 7.1. Primary objective).

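### Nephrectomy and radiotherapy are compared as baseline characteristics, but no rule ties their dates to the start of axitinib

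*SAP*

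**What the plan says.** SAP 6, in the block on the clinical history of the renal cancer, lists "Nephrectomy (Yes/No/Unknown" and "Radiotherapy (Yes/No/Unknown". Each has a single date field, "Date (Date/Unknown", and neither has a time limit. Protocol 5 starts the observation period at diagnosis and has it "ending at the time of inclusion in the study, or the death of the patient if this occurs first". The only data cut-off in SAP 7 is the inclusion or consent date.

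SAP 7 uses the procedure dates for intervals such as "Time (months) between first diagnosis and radiotherapy". Cases dated on or before diagnosis are listed and left out of that descriptive interval. Neither date is compared with axitinib start.

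SAP 9.2 (primary objective) counts as baseline the "baseline clinical characteristics (clinical history of renal cell carcinoma, first-line treatment, other treatments prior to axitinib", and adds: "The baseline clinical characteristics will be statistically compared according to membership to each one of the two extreme treatment response groups". SAP 7.1 names "Previous nephrectomy (yes and no" among the association factors and restricts the logistic model, in words, to factors that precede axitinib. Radiotherapy is not in the 7.1 list.

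**The concern.** A baseline factor in this study has to be settled before axitinib starts, because the response groups are defined by what happens afterwards. A procedure done during or after axitinib may be a consequence of the course of disease, or may simply reflect how long the patient was observed. If it is tabulated and tested as baseline, a difference between the groups can appear where none existed before treatment.

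The exposed analysis is the SAP 9.2 comparison under the primary objective, tested at 0.05 two-sided with no multiplicity adjustment (SAP 4). For nephrectomy, the 7.1 association analysis is exposed as well.

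**Working it through.** **1. The texts side by side**

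- *Anchoring.* Other SAP 6 items are tied to a time point: risk criteria before first line, at axitinib start and at axitinib discontinuation, and treatments before axitinib. The two procedure fields are not.
- *Where later radiotherapy would go.* The subsequent-treatment fields in SAP 6 ask for drug, starting dose and treatment line, which fit systemic therapy. SAP 6 says that it details every CRF variable, and it shows no other field for radiotherapy.
- *Use of dates.* Both are set against first diagnosis only.
- *Use in analysis.* The whole clinical history block is tested between groups as baseline.

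The dates are collected, so what is missing is a derivation rule. Data are missing only where the date is unknown.

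**2. Scale (illustration only)**

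The plan states no figure on this point, so there is none to reproduce. Inputs from the documents are about 60 patients (Protocol 8.5) and a ratio of about 2:1 (Protocol abstract, study population), giving 60 × 2/3 = 40 responders and 60 × 1/3 = 20 refractory patients. All else is assumed: true radiotherapy prevalence before axitinib is 20% in both groups, so the true odds ratio is 1. Rejection rates come from full enumeration of the 40 v 20 tables with an uncorrected chi-squared test.

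*A. Later radiotherapy accrues with observation time.* Recorded prevalence = 1 − 0.80 × exp(−rate × months), with a rate of 0.5–2% per month and 18–30 v 6–8 months after start.

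- At 1% per month and 24 v 6 months: 1 − 0.80 × exp(−0.24) = 0.371 and 1 − 0.80 × exp(−0.06) = 0.247. Odds ratio = (0.371/0.629)/(0.247/0.753) = 1.8.
- Smallest (0.5%, 18 v 8 months): 0.269 v 0.231, odds ratio 1.2.
- Largest (2%, 30 v 6 months): 0.561 v 0.290, odds ratio 3.1. This needs 1 − exp(−0.6) = 45% of unirradiated responders to be irradiated later.

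*B. Later radiotherapy follows progression.* All refractory patients have progressed. Let f be the share of progressing patients irradiated (10–30%) and g the share of responders who progressed (50–100%). Responders: 0.20 + 0.80 × f × g. Refractory: 0.20 + 0.80 × f.

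- f = 0.3, g = 0.5: 0.32 v 0.44, odds ratio (0.32/0.68)/(0.44/0.56) = 0.60.
- g = 1: equal prevalences, odds ratio 1.0.

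*C. Equal later use,* 10% of the unirradiated in each group: 0.20 + 0.80 × 0.10 = 0.28 in both, odds ratio 1.0.

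| Case | Recorded, responders v refractory | Odds ratio | P<0.05 |
|---|---|---|---|
| A, smallest | 27% v 23% | 1.2 | 6% |
| A, middle | 37% v 25% | 1.8 | 16% |
| A, largest | 56% v 29% | 3.1 | 53% |
| B, furthest from 1 | 32% v 44% | 0.60 | 15% |
| C | 28% v 28% | 1.0 | 5.1% |
| Dated before start only | 20% v 20% | 1.0 | 4.7% |

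In case A, prevalences before axitinib of 10% and 30% give odds ratios of 1.4–4.1 and 1.2–2.6.

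**The case against.** The best defence is that the plan already intends a limit before axitinib. Nephrectomy is labelled as previous, the model is confined in words to factors before axitinib, and both procedures sit in a history block that comes ahead of separate blocks for axitinib and subsequent treatment. A site might well read the fields that way. This stands as evidence of intent. It does not supply a rule: no derived variable implements either limit, the restriction in 7.1 governs the model and not the 9.2 comparison, and radiotherapy carries no such label.

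Three stronger readings are tempting and should be resisted.

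- *The fields are ever/never up to inclusion.* SAP 6 does not say so. This is inferred from the missing limit and the observation window.
- *Longer observation must produce more Yes answers among responders.* That holds only if later use accrues at a similar monthly rate in both groups. If radiotherapy follows progression, the distortion reverses or vanishes.
- *A late nephrectomy will enter the logistic model.* That would breach the restriction stated in 7.1. What is missing is the check that would catch it. Whether radiotherapy could reach the model's screen at all is unclear, since it is not a listed factor.

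The study is also exploratory, with no pre-specified hypotheses. This limits the weight of any one test, but it does not make a post-treatment event a baseline factor.

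**Conclusion.** The gap is real: as written, the SAP can count a nephrectomy or radiotherapy course done on or after axitinib start as a baseline characteristic in the primary group comparison, and nothing in it would detect this. The case is strongest for radiotherapy and weaker for nephrectomy.

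The documents do not show that bias will occur or which way it would run. Under the assumptions above, the false odds ratio lies between about 0.6 and 3.1, with false-positive rates at 0.05 from nominal to 53%. The upper end needs heavy later use among responders. All figures are for radiotherapy; none was derived for nephrectomy. The point warrants a cheap correction to the SAP and does not by itself invalidate the comparison.

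**What to change.** In SAP 7, derive *nephrectomy before axitinib start* and *radiotherapy before axitinib start*, each Yes only when the recorded procedure date is earlier than the axitinib start date. Use these in 7.1, in the 9.2 comparison and in any model, and list procedures dated on or after start separately.

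Three date rules should go with them:

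- A Yes with an unknown date is treated as missing.
- So is a Yes with a partial date completed under SAP 8 (15 June when only the year is known, the 15th when only the day is missing) if the possible range spans axitinib start. One sensitivity run counts both kinds as Yes.
- The CRF holds one radiotherapy date and does not say that it is the first course. Radiotherapy dated after start should be queried or flagged for an earlier course before it is coded No.

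The cost is two derivations, these rules and a few queries; no new CRF field is needed. A few patients will become missing for these two variables.
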